Hypoth 1.1 CFS patients assigned to PP-T-CBSM will show greater reductions in average CDC-based Symptom Frequency and Duration compared at 5- and 9-month follow-up vs. those in T-HI.

Hypoth 1.2 CFS patients assigned to PP-T-CBSM will show decreases in CFS symptoms of diarrhea, fatigue, muscle pain, unrefreshing sleep, sinus problems and general weakness, at 5- and 9-month follow-up vs. those assigned to T-HI.

SECONDARY AIMS

AIM 2: To determine if T-CBSM intervention improves di-urnal cortisol regulation and immune regulation (pro-inflammatory:anti-inflammatory cytokine ratio ([IL-1B+ IL-6 + TNF-x]:[IL-13 + IL-10]) relative to participants in the T-HI condition and how these changes relate to CFS symptoms.

Hypoth 2.1. CFS patients assigned to PP-T-CBSM will show greater reductions in pro-inflammatory: anti-inflammatory cytokine level ratio at 5- and 9-month follow-up compared to those assigned to T-HI.

Hypoth 2.2. CFS patients assigned to PP-T-CBSM will show greater increases in the AM-PM negative slope of salivary cortisol at 5- and 9-month follow-up compared to those assigned to T-HI.

Hypoth 2.3. The magnitude of reductions in CFS symptom frequency and severity from baseline

to 9 month follow-up will be associated with greater reductions in the pro-inflammatory: anti-inflammatory cytokine ratio and greater increases in the AM-PM salivary cortisol negative slope.

AIM 3: To test whether reductions in total and specific CFS symptoms and neuroimmune process indicators in PP-T-CBSM are associated with greater improvements in patient/partner psychosocial functioning (decreased stress, depression and social disruption and increased social support).

Hypothesis 3.1 Patients/partners assigned to PP-T-CBSM will show greater reductions in stress, depression and social disruption, and greater increases in social support at 5- and 9-month follow-up compared to those assigned to T-HI.

Hypothesis 3.2 The magnitude of reductions in CFS symptoms and pro-inflammatory cytokines and increases in the AM-PM salivary cortisol slope from baseline to 9 month follow-up are associated with greater decreases in stress, depression and social disruption and greater increases in social support.

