1. Scope, Epidemiology, Etiology and Impact of CFS. According to the CDC (1) the overall prevalence of Chronic Fatigue Syndrome (CFS) in the U.S. is 235 per 100,000 persons (95% confidence interval, 142327 per 100,000 persons). Up to 80% of those affected are women (2). These individuals suffer from severe fatigue that impairs daily activity, diminishes quality of life for years and has no known cure (3). CFS symptoms bring about severe limitations in the lifestyle behaviors, and vocational activities of previously vital, productive and successful individuals (4). Symptoms include debilitating fatigue, low grade fever, lymph node pain and tenderness, pharyngitis, myalgias, arthralgias, cognitive difficulties and mood changes (5, 6, 7). Current medical treatments focus on symptom management (antidepressants, antifungals, antihistamines, antivirals, CNS depressants or stimulants, immunoglobulins, anti-inflammatories, anticonvulsants, macro-vitamin regimens) (8) but are not curative. Symptoms may emerge at unpredictable times, one of the features of CFS that makes it particularly stressful. CFS represents an economic burden for society (e.g., high rates of unemployment due to disability) and healthcare institutions (9). Hypothetical initiating events for CFS include infections, psychiatric trauma and exposure to toxins though etiology remains unknown (10). Many of the symptoms are inflammatory in nature and have prompted a theory of infection induced illness (11, 12) that presents with acute onset of illness, with systemic symptoms similar to influenza infection that do not subside (13). These observations have led to reports of associated microbial infection or reactivation of latent viral infections (11, 14, 15, 16). There is growing evidence that CFS patients reliably show abnormalities on several indices of immune functioning (e.g., elevated IgG, impaired natural killer cell activity, NKCA, 17), elevated levels of circulating cytokine peptides and/or mRNA (18), and abnormalities in the numbers and activation states of certain lymphocyte subpopulations (17, 19, 20, 21 – 25). Recent work in the U.S. isolating a gammaretrovirus virus (XMRV) in the etiologic pathway of CFS adds strength to the notion of a chronic immune system activation (26) though this XMRV finding has failed to replicate in a UK population study (27).

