3. Immune Dysregulation in CFS. Our model proposes that CFS involves an immunologic dysregulation (due to virus infection or unknown causes) characterized by chronic lymphocyte activation with elevated expression of lymphocyte activation markers, episodic increased expression of cytokines such as tumor necrosis factor (TNF)-a and b peptide and soluble receptor in serum/plasma, and mRNA in circulating lymphocytes, and associated decrements in cellular immune function, which may in turn, hamper anti-viral immunity and fail to eradicate viral infections thus promoting further immune activation (39, 28). We showed that CFS patients with the greatest fatigue severity and lowest vigor had lower NKCA and greater signs of lymphocyte activation (increased CD2+CD3+CD26+ T-cells). TNF-a and soluble TNF receptor-type I (sTNF-RI) were greater in the low NKCA group vs the normal NKCA group (40). Thus elevated pro-inflammatory cytokines such as TNF-a may accompany both decrements in antiviral immunity (via NKCA) and greater CFS symptom expression. TNF-a and b are primary modifiers of the inflammatory and immune reactivation in response to injury or infection, and are primarily produced by macrophages. Overproduction, inappropriate expression of TNF, and TNF injections have been associated with fever, slow-wave sleep induction and appetite suppression (41- 44), which may underlie the fatigue, lassitude and excessive sleepiness associated with CFS (45). We found that CFS patients show significantly elevated TNF- a and b levels compared to controls (20, 18). CFS symptoms may be part of a complex referred to as "sickness behavior" wherein fatigue, sleep disturbances, pain and other CFS-like symptoms are believed secondary to chronically elevated levels of pro-inflammatory cytokines (IL-1, IL-6, TNF) (46, 47). This pattern of increased pro-inflammatory cytokine production may be triggered by antigenic stimulation (e.g., viral infection) and maintained by stress/mood-related hypothalamic-pituitary adrenal (HPA) axis alterations (e.g, flattened di-urnal secretion of glucocorticoids, and/or decreased glucocorticoid sensitivity in immune cells that produce pro-inflammatory cytokines) (48). Sickness behavior symptoms and accompanying elevations in pro-inflammatory cytokines (e.g., TNF) are compatible with the symptom picture and cytokine patterns identified in CFS patients by our group (49).

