(only participants who live outside our catchment area) will be administered to screen for signs of gross intellectual impairment or attention problems that could threaten the validity of baseline and follow-up assessments. If participant is eligible an appointment will be made to proceed with the consent process and baseline interview instructions. During the face to face visit the interviewer will review and provide a copy of the consent form to both the CFS patient and their identified partner. Participants will be given time to carefully read the consent form and ask any questions about the study. If participants live outside our catchment area they will be sent an electronic copy of the consent forms. CFS patients and their partners will be contacted via telephone to review the consents and answer any questions pertaining to the study. If participants agree to participate they will be asked to sign the consent forms and send them to our office via email (pdf), fax or regular mail. Their consent date will be recorded in our records during the telephone call in which we review the consent and will later be reconfirmed by the signed hard copy. Once participants consent to participate in the study the participants will be provided with instructions on how to complete the baseline interview via SurveyMonkey, a data collection program (please refer to section 4.4A). The core battery for the CFS patient will consist of the following focus areas: 1) Demographic information; 2) Lifestyle behaviors; 3) Physical factors related to CFS; 4) History of CFS; 5) Service utilization; 6) Perceived life stressors; 7) CFS symptoms; 8) Psychological functioning; 8) Social support; 9) Quality of patient-partner relationship; and 10) Changes in perceived CBSM skills. The core battery for the identified CFS partner will consist of demographic information, psychological functioning, social support, quality of patient-partner relationship, and changes in perceived CBSM skills. The time duration of the interviews is estimated to be 1-2 hours for the CFS participants and 30 minutes for the partner. Participants will be asked to complete a project evaluation questionnaire at the second (5 month) and third (9 month) interview and is estimated to take 15-20 minutes to complete. Participants (chronic fatigue patients only) will also be asked to collect four saliva samples on two consecutive days and provide us with a blood sample (about 2 ounces) at each measure point (baseline, about 5 month and about 9 month follow-ups). Chronic fatigued patients will be provided with a saliva kit and detailed instructions on how to collect the saliva and blood draw collection protocol (e.g. lab schedules and appointments and locations). For those participants who live outside our catchment area they will be sent a package via FedEx with instructions on how to collect the saliva samples and visit one of our contract labs near their area. Once they collect their samples they will send them to our lab processing center at the Papper Clinical Immunology Laboratory at the University of Miami ([name]).

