
Intervention Protocol:

After participants complete the interviews, and chronic fatigue patients complete the collection of saliva and blood, they will open an envelope that will advise them of the group they were randomly assigned to (PP-T-CBSM or T-HI). Participants who live outside our catchment area will be contacted to inform them of their randomization group. Randomization will occur in waves of eight, four dyads will be randomized to PP-T-CBSM and 4 to P-HI). Subjects randomized to PP-T-CBSM will receive 10 weeks of group intervention as described herein. A total of 4 dyads (CFS patient and their identified partner) will meet once weekly by videophone for approximately a one hour session at a mutually convenient set time. The content of the PP-T-CBSM protocol will comprise two broad domains: Cognitive, behavioral and interpersonal skills training and relaxation/imagery. The Cognitive, Behavioral and Interpersonal skills component presents information concerning stressors and stress responses from a biopsychosocial perspective. The initial 5 weeks emphasize: (1) the importance of appraisals in the stress response and in symptom occurrence; (2) understanding automatic thoughts and cognitive distortions; (3) identifying and monitoring automatic thoughts; (4) disputing and restructuring cognitive distortions into more rational thoughts, and (5) learning adaptive problem-focused and emotion-focused coping skills. By monitoring automatic thoughts associated with negative emotions, participants increase their awareness of cognitive appraisals that precede changes in emotion. Stressors of primary importance in this study are those concerning the physical symptoms of CFS and the losses associated with the illness. Participants learn how automatic thoughts, including cognitive distortions may contribute to symptom magnification and ensuing feelings of loss of perceived control. The remaining 5 weeks focus on

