Treatment fidelity will be monitored by audio taping a random sample of the intervention sessions. Participants will be asked for their permission to be audio taped at the end of the consent form. If participants do not feel comfortable being audio taped this will not affect their participation in the study. Those participants refusing to be audio taped will not be audio-taped at any point of the intervention. In addition audio tapes will be destroyed upon participant's request.

Follow-up Interview Protocol:

Upon completion of the 10 week program for both PP-T-CBSM and T-HI, participants will be contacted by a study staff member to coordinate the 5 (approximate) month follow-up interview. Participants will be sent their interview via email to complete electronically using SurveyMonkey. They will also be mailed a saliva kit with instruction on how to complete it. Participants will have a 2-3 week window to complete the interview and saliva collection before scheduling a blood draw at one of our lab locations. Participants who live outside our catchment area will follow the same lab collection protocol outlined above. This procedure will be repeated in four months when the last collection point at about the 9 month follow-up.

Blood Draw Protocol:

Chronic fatigue patients will be asked to provide about 2 ounces of blood at each time point. The blood collection will be conducted at one of the designated lab locations. An appointment will be made by one of our staff members who will also be meeting the participant at the lab location. No identifying patient information will be shared with the lab sites; appointments will be made using the study name and subject ID and pre-printed labels with subject's ID will be used on collected blood samples. A member of the study staff will be with the participant at all times to insure that the blood collection is conducted safely. The saliva samples and blood sample will be taken to [name] Lab (E. M. Papper Laboratory of Clinical Immunology). Participants who live outside our catchment area will be asked to visit one of our contracted lab (for example Labcorp) in their area. Participants will be sent a package with detail information about the blood draw protocol (including lab request forms, tubes and instructions to the lab) and how to send back the samples to [name] Lab.

Technical Support and Installation of the VideoPhone System:

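### No maximum interval is set between interview, saliva and blood, so cytokines can be measured weeks from the symptoms, psychosocial scores and cortisol that Hypotheses 2.3 and 3.2 relate to them

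*Combined protocol and SAP*

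**What the plan says.** **Follow-up.** Section 4.4, Follow-up Interview Protocol, sets the order of collection at about 5 months: "Participants will have a 2-3 week window to complete the interview and saliva collection before scheduling a blood draw". For the 9-month assessment it adds: "This procedure will be repeated in four months". The Blood Draw Protocol makes the draw a booked visit ("An appointment will be made by one of our staff members who will also be meeting the participant at the lab location") but gives no limit on how long after the interview or saliva it may fall.

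**Baseline.** The Intervention Protocol says only that everything precedes disclosure of allocation: "After participants complete the interviews, and chronic fatigue patients complete the collection of saliva and blood, they will open an envelope". No window or maximum gap is stated.

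**Sources of the measures.** Under Study Procedures, patients are to "collect four saliva samples on two consecutive days" at each time point. Symptoms, psychological functioning and social support all sit in the patient's core battery. Cytokines come from blood.

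**Hypotheses.** Hypothesis 2.3 holds that symptom reductions from baseline "to 9 month follow-up will be associated with greater reductions in the pro-inflammatory: anti-inflammatory cytokine ratio" and with a steeper cortisol slope. Hypothesis 3.2 relates changes in symptoms, cytokines and cortisol over the same period to changes in stress, depression, social disruption and support.

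**Disease model.** Section 4.2, subsection 3, speaks of "episodic increased expression of cytokines such as tumor necrosis factor". Subsection 1 says: "Symptoms may emerge at unpredictable times, one of the features of CFS that makes it particularly stressful". Part B of the same section mentions unpredictable flare-ups as a reason why patients declined clinic-based groups.

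**Analysis.** The Study Design text names medications, physical activity and possible confounders as controls. It does not name the time between measures.

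**The concern.** A nominal time point can combine a questionnaire from the start of the window, saliva from its end, and blood drawn later still. Hypothesis 2.3 asks whether these quantities move together. To the extent that cytokines and symptoms fluctuate over weeks, as the plan's own model suggests, values taken at different moments share less of that fluctuation and their correlation shrinks.

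What is at stake is how the mechanism results can be read. A weak or null association between cytokine change and symptom change could mean that the neuroimmune model fails, or that the samples were mistimed. Unless the three dates are recorded and used, the analysis cannot separate the two. The plan presents the neuroimmune mechanism as one of the study's main innovations, so this matters even though the hypotheses are secondary.

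**Working it through.** **1. Gaps the schedule permits.**

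| Pair | Source | Gap permitted at follow-up |
|---|---|---|
| Patient symptoms and patient psychosocial scores | same core battery | none planned |
| Interview and saliva | one shared window | 0 to about 21 days |
| Interview or saliva, and blood | blood booked after the window's tasks | a few days (assumed minimum) to more than 21 days; no upper limit stated |

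The pairs exposed are therefore cytokine-symptom, cytokine-cortisol and cytokine-psychosocial, and to a lesser extent cortisol with symptoms or psychosocial scores.

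**2. Is there a planned figure to reproduce?** No. The documents give 150 patients with 124 expected at the final assessment (124/150 = 82.7%). They give no alpha, power, effect size, standard deviation or correlation for these hypotheses.

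**3. Illustration.** From the documents: n = 124. Assumed: true change correlation r = 0.30, two-sided alpha 5%, lag 3 weeks at follow-up and none at baseline, and a correlation that is wholly episodic and decays with half-life h = 2, 4 or 8 weeks.

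- Decay over the lag: k = 0.5^(3/h).
- Hypotheses 2.3 and 3.2 use change from baseline to 9 months. Suppose the episodic parts at the two ends are independent and equally variable. Each end then contributes half the covariance of the two change scores. Only the follow-up half is multiplied by k, so the change correlation is multiplied by m = (1 + k)/2.
- Power by Fisher's z: Φ(atanh(r·m) × √(124 − 3) − 1.96), with √121 = 11.

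With no lag: atanh(0.30) × 11 = 3.405, and Φ(1.445) = 93%.

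| h (weeks) | k | m | r·m | atanh(r·m) × 11 | Power |
|---|---|---|---|---|---|
| 2 | 0.354 | 0.677 | 0.203 | 2.265 | 62% |
| 4 | 0.595 | 0.797 | 0.239 | 2.683 | 77% |
| 8 | 0.771 | 0.886 | 0.266 | 2.994 | 85% |

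**4. If half the correlation reflects sustained change.** The multiplier becomes 0.5 + 0.5m = 0.838, 0.899 or 0.943. The correlation is 0.252, 0.270 or 0.283, and power by the same formula is 81%, 86% or 89%.

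**5. What a 7-day lag would give on the same footing** (follow-up only, wholly episodic). k = 0.5^(1/h) = 0.707, 0.841 or 0.917; m = 0.854, 0.920 or 0.959; r·m = 0.256, 0.276 or 0.288; power = 82%, 88% or 90%. Most of the illustrated loss is recovered, but not all of it.

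**The case against.** The case on the other side is substantial, and most of it stands as a limit on the claim.

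- **The window is a permission.** A reader might infer that the measures are taken weeks apart. The text does not say so. A patient may finish interview and saliva together and have blood drawn days later, and no actual lag appears in the documents. They support only that the gap can be weeks.
- **Hypothesis 3.2 is only partly exposed.** A reader might take the whole of it to be compromised. Patient symptoms and patient psychosocial scores come from the same interview, so those pairs have no planned gap.
- **A larger power loss is tempting.** Applying the 3-week lag at baseline as well would multiply the correlation by k itself and give 22%, 51% or 74%. The 2-3 week window is stated for follow-up only; the baseline interval is unspecified.
- **The model is not purely episodic.** Section 4.2, subsection 3, also describes chronic lymphocyte activation and chronically raised pro-inflammatory cytokines. A lag of some weeks would hardly disturb that component, nor a treatment effect sustained to 9 months.
- **Relevant material is not in the text.** The symptom recall period and the detailed saliva and blood instructions are not shown. A recall period of several weeks would reduce the misalignment.
- **Limiting the main analysis to closely timed sets would do harm.** It would select patients on behaviour after randomisation, probably losing those in a flare.

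What the objection does not remove is that the stated procedure puts blood last, after a window of 2-3 weeks, with no upper limit and no planned use of the interval in the analysis.

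**Conclusion.** The concern holds in a limited form. At both follow-ups the stated order allows cytokines to be measured weeks from the symptoms, cortisol and psychosocial scores they are related to. No maximum interval is set at any of the three time points. This can weaken the associations in Hypothesis 2.3 and the cross-source parts of Hypothesis 3.2.

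The true size cannot be calculated from the documents. The 62% to 85% range against 93% rests on an assumed correlation, assumed half-lives, a 3-week lag for every patient at follow-up, closely timed baseline measures and a wholly episodic correlation. A sustained component makes the loss smaller; a lag at baseline as well would make it larger.

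A reader might go further and conclude that Aim 2's mechanism question cannot be answered. That does not follow: a weakened association is harder to interpret, but it is still informative. The primary outcome and the between-group comparisons in Hypotheses 1.1, 1.2, 2.1, 2.2 and 3.1 do not depend on the measures being simultaneous. This is a weakness in secondary mechanism analyses that is worth correcting because the correction is cheap.

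**What to change.** 1. At all three time points, book the blood draw first. Place the two saliva days and the online interview close to it, within a target interval stated in the protocol. Seven days is offered as an example; it is a proposal and not a figure from the documents.
2. Record the dates of interview, saliva and blood for every patient and time point.
3. Keep all data in the main analyses, including sets outside the target interval.
4. Pre-specify a sensitivity analysis for the cytokine and cortisol associations in Hypotheses 2.3 and 3.2, either adjusted for the interval between measures or restricted to sets within the target. Symptom-psychosocial pairs from the same interview need no such restriction.

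Cost: a change of scheduling order and a few protocol sentences. Staff already book the draw for patients within the catchment area, and saliva kits are already mailed at follow-up, so no new visit, kit or laboratory is needed. The downside is slightly tighter scheduling for fatigued patients with unpredictable symptoms, and some sets will still fall outside the target interval.
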